4.5. SITES

Site Name/s	The study site is Sydney LHD. Teams involved in the study will be four adult Community Mental Health 'Core' Teams at Canterbury, Croydon, Camperdown and Marrickville
Site Contact/Investigator	[name]
PHO	YES
If a non-PHO is an EEA in place?	N.A.
Study Procedures	
Procedures have been developed in consultation with site team leaders and staff and will be the consistent across all four mental health teams. The number of active consumers with each team varies from 278 to 448. It is anticipated that each team will recruit approximately one-quarter of the total sample, with larger teams recruiting slightly more than smaller sites.
 
Care coordinators at each team will identify and approach potential study participants. They will be given written information to give to the consumer. With the consumer’s permission, care coordinators will provide the research team with contact details of consumers who are interested in participating in the study.
 
A research officer will contact these potential participants to explain the study, answer any questions, and obtain informed consent. In intervention sites, participant consumers will be asked to approach their GP to be part of the project or consent to the research team doing so on their behalf to recruit GPs to the study.
 
For consumers in the intervention group, if GPs provide consent to participate in the study, they and their patient are enrolled in the study and an appointment is made to install the shared care software in the practice’s computer and arrangements will be made to train the GP in its use.
 
Consumers in the comparison group will receive usual care. If their GP decline to be involved in the study, these consumers will remain enrolled in the study for intention-to-treat analysis.
 
Consumer participants will participate in a baseline survey which is repeated 3 months after their usual shared care appointment, or 3 months after 30 June for those consumers who did not attend their shared care appointment. These interviews will be conducted via telephone, online or face-to-face, depending upon the preference of each consumer.
 
All consumers will be invited to participate in a qualitative interview after the 3-month survey.
 
Care Coordinators and GPs will also be interviewed after the intervention period.

All survey and interview data, and data extracted from HealthNet (including MBS/PBS items) and medical records will be entered into a SLHD REDCap data base. De-identified data from external repositories (ICOD) will be saved in secure password protected OneDrive files at UNSW Sydney. Data for the economic studies will be saved in secure password protected OneDrive files for assembling and analysis at The University of Sydney, and outputs (during and post analysis stage) will be stored on the SLHD REDCap.

5. STUDY PARTICIPANTS

5.1. INCLUSION CRITERIA

1. Consumers from SLHD Adult Community Mental Health 'Core' Teams in Canterbury, Croydon, Camperdown and Marrickville.
2. Age: 18+ years
3. Engaged in shared care or willing to commence a shared care arrangement before the baseline survey.
4. Intervention group: Has a GP engaged in shared care who consents to participate in the study and to have the electronic care plan installed
5. Willing to provide informed consent and willingness to participate and comply with the study requirements.

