
Study Procedure
	
 1.SLHD Adult Community Mental Health 'Core' Teams will be randomised to – 1 of Canterbury or Croydon and 1 of Camperdown or Marrickville will be randomly allocated to the intervention group and the other will receive delayed intervention 2.500 People with severe mental illness (PWSMI) who have contact with these teams and who are identified as suitable by the Core team staff member who is their care coordinator during routine visits will be given written information about the study. With the consumer’s permission, care coordinators will provide the research team with contact details of consumers who are interested in participating in the study. 3.A research officer will contact these potential participants to explain the study, answer any questions, and obtain informed consent. 4.Participant consumers will be asked to approach their GP to be part of the project OR consent to the research team doing so on their behalf to recruit GPs to the study. 5.If GPs provide consent to participate in the study, they and their patient are enrolled in the study and an appointment is made to install the INCA shared care software in the GP practice’s computer and arrangements will be made to train the GP in its use and a baseline survey is conducted with the consumers and their shared-care GPs. 6.Consumers in the intervention group will have their physical health care coordinated through an online shared care plan. 7.Consumers in the comparison group will receive usual care. 8.If GPs withdrew consent to participate in the study, their patient will remain enrolled in the study and will be able to participate in a repeat interview 3 months after their reported usual shared care. 9.Consumer and GP participants will participate in a repeat interview 3 months after their reported usual shared care. If any consumer does not have a shared care appointment/follow-up since baseline, they will be invited to participate in the repeated interview three months after 30 June 2023 (i.e., 3 months after the deadline for the intervention to be implemented). 10.With consent and approval, relevant health service use and clinical data will be extracted from medical records held by GPs, datasets held by SLHD, HealthNet (including MBS/PBS items), and the NSW Ministry of Health (ICOD). 11.A subset of consumers will be invited to participate in a qualitative interview after 3 months of their reported usual shared care. 12.A subset of SLHD mental health clinicians (Care Coordinators and shared care clinicians) and GPs will be interviewed after the intervention period.

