4. STUDY DESIGN

4.1. DESIGN / STUDY TYPE

This is a pragmatic cluster randomised controlled trial. The unit of randomisation is the team. The teams are four of the five Adult Community Mental Health 'Core' Teams in SLHD (Table 1). Randomisation will be stratified by sector (Eastern and Western): One team from each sector will be randomised to the intervention group, the other team will be allocated to the comparison group. The comparison group Teams will receive the intervention after the 3-month data collection is complete.

As there are only two teams per sector in the study, randomisation will be done by a person independent from the study by flipping a coin.

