5. GPs can consent verbally (Appendix 11.6) or by signing a written consent form (Appendix 11.3). GPs will be offered reimbursement for their participation in the study (\$100 shopping voucher or cash for participating in each component of the study). Recruitment materials include a letter of invitation from the head of the mental health service in the LHD (Appendix 15.1), a letter from the GP's patient informing the GP that s/he has consented to be in the study and inviting the GP to also consent to be in the study (Appendix 15.2), GP participant information abbreviated (Appendix 15.3) and in full (Appendix 10.2).

9. *What happens if a GP does not want to participate?*

If a GP does not want to participate in the trial, neither they nor their patients who are engaged with the mental health service (MHS) will be given access to the online shared-care tool. Consumers of these GPs can still provide baseline data for the study and will be followed up for the study. Communication between the GP and the MHS will continue as usual, which is generally via letters and faxes.

10. How will participants be recruited to the qualitative interview?

Participants from both groups will be invited to participate in semi-structured qualitative interviews. This will include consumers and their carers, and health care providers (including MHS staff and GPs).

Consumers will be invited to express interest in themselves and/or their carers being interviewed for the study via an invitation within the consumer survey. Contact details will be requested so the study team can contact the consumer and/or their carer.

The research team will contact the consumers who expressed interest and any carers who were nominated by consumers to recruit them to the qualitative interviews.

GPs will be invited to express interest in being interviewed for the study via an invitation within the GP survey. A similar process to that for consumers will be used to contact those GPs who expressed interest in being interviewed.

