6.5. PARTICIPANT ENROLMENT

Potential participants will be enrolled into the study after the informed consent process has been completed and the participant has been assessed to meet all the inclusion criteria and none of the exclusion criteria. Study participants will receive a study enrolment number and this will be documented on all study documents.

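### GP consent and software installation is an entry condition for the intervention arm only, applied after teams are allocated, and it conflicts with the rule that consumers of non-participating GPs are followed up

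*Protocol*

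**What the plan says.** **Order of events.** Teams are the unit of randomisation (section 4.1): "One team from each sector will be randomised to the intervention group, the other team will be allocated to the comparison group". The synopsis lists allocation as step 1 of the study procedure, "1 of Canterbury or Croydon and 1 of Camperdown or Marrickville will be randomly allocated to the intervention group", and the approach to consumers from step 2.

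**Entry rule, intervention arm.** Section 5.1, criterion 4, repeated in the synopsis: "Intervention group: Has a GP engaged in shared care who consents to participate in the study and to have the electronic care plan installed". Section 6.5 allows enrolment only when "the participant has been assessed to meet all the inclusion criteria and none of the exclusion criteria". Section 4.5 says the same for intervention consumers: "if GPs provide consent to participate in the study, they and their patient are enrolled in the study". Synopsis step 5 ties enrolment to GP consent without naming an arm.

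**Entry rule, comparison arm.** Criterion 4 has no counterpart. Section 4.5 says of comparison consumers: "If their GP decline to be involved in the study, these consumers will remain enrolled in the study for intention-to-treat analysis".

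**Consumers of GPs who do not take part.** Section 5.3, item 9, without restriction by arm: "Consumers of these GPs can still provide baseline data for the study and will be followed up for the study". Synopsis step 8 covers a different case, withdrawal after consent: "If GPs withdrew consent to participate in the study, their patient will remain enrolled in the study".

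**Analysis.** Section 8.2 plans an intention-to-treat analysis. It defines drop-out as discharge from shared care or withdrawal of consent, so GP refusal is not covered. Its costing part defines the economic comparator by non-receipt of the intervention rather than by allocation.

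**The concern.** An intervention-team consumer whose GP declines is ineligible under sections 5.1, 6.5 and 4.5, yet is in the study under section 5.3. No passage says in which arm such a consumer is analysed, and the receipt-based economic comparator would place them with usual care.

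This goes beyond wording. If criterion 4 is followed, the intervention arm contains only consumers whose GP agreed to install a shared-care tool, while the comparison arm contains consumers of willing and unwilling GPs alike. The filter acts with the arm known. It selects on the GP, who largely generates the primary outcomes: Table 9 takes screening from GP records and prescribing from GP records and HealtheNet, and the third outcome is consumer-reported advice or referral from the GP. If engaged GPs deliver or record preventive care differently, or improve at a different pace, the arms can differ without any effect of the tool. Imputation cannot restore consumers who were never enrolled. The planned adjustments (sections 5.4 and 8.2) concern consumer characteristics and variables found to differ at baseline.

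**Working it through.** **1. The rules side by side, for a consumer whose GP declines at the first approach**

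| Source | Intervention team | Comparison team |
|---|---|---|
| 5.1 criterion 4 with 6.5 | not eligible | eligible |
| 4.5 | enrolled if the GP consents | remains enrolled for intention-to-treat |
| 5.3 item 9 | baseline and follow-up, no tool | baseline and follow-up, no tool |
| 8.2, economic comparator | counted with usual care | usual care |

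The intervention column contradicts itself; the comparison column does not.

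**2. What enforcing criterion 4 does when the tool has no effect**

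Let c be the share of consumers whose GP would consent, a and b the usual-care outcome rates for consumers of consenting and non-consenting GPs, and Δa and Δb the changes in those rates over time. The protocol gives none of these. Assume outcomes are observed for everyone enrolled.

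- Post-intervention levels only: a − [c·a + (1 − c)·b] = (1 − c)(a − b).
- Change from the earlier period, as in section 4.4 and Table 9: (1 − c)(Δa − Δb).

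If the gap between GP types is stable, Δa = Δb and the second expression is zero. If trends differ, it is not. For scale only, an assumed c of 0.3 to 0.9 and an assumed gap of 5 to 20 points make the first expression run from 0.1 × 5 = 0.5 points to 0.7 × 20 = 14 points, against the planned 20-point difference. That range applies only to a post-period comparison with complete data.

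**3. The protocol's sample size (sections 4.2 and 8.1)**

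Inputs: 30% against 50%, α = 0.05 (taken as two-sided), power 0.80, design effect 2, 500 recruited with 20% loss.

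- n per group = (1.960 + 0.842)² × (0.30 × 0.70 + 0.50 × 0.50) / 0.20² = 90.3, rounded up to 91. This reproduces the stated figure.
- 91 × 2 = 182 per group, 364 in total. The protocol states 180 and 360, a rounding difference.
- 500 × 0.8 = 400 followed, or 200 per arm if the arms are equal.

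**4. Power when everyone is kept by allocated team**

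Assume the 20-point effect occurs only where the GP consents, so the intervention rate is p₂ = 0.30 + 0.20c. The effective n per arm is 200 / 2 = 100. With d = 0.20c and p̄ the mean of 0.30 and p₂:

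Power = Φ{[d − 1.96·√(2p̄(1 − p̄)/100)] / √[(0.30 × 0.70 + p₂(1 − p₂))/100]}

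For c = 0.5: p₂ = 0.40, p̄ = 0.35, the standard errors are 0.0675 and 0.0671, and (0.10 − 0.132)/0.0671 = −0.48, giving 0.32.

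| Uptake c | Difference | Power |
|---|---|---|
| 1.0 | 20 points | 0.83 |
| 0.9 | 18 points | 0.75 |
| 0.7 | 14 points | 0.54 |
| 0.5 | 10 points | 0.32 |

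These figures accept the protocol's design effect of 2 as given.

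**The case against.** **The arms need not be filtered at all.** Section 5.3 follows up consumers of non-participating GPs, synopsis step 8 keeps those whose GP withdrew, and section 8.2 does not list GP refusal as drop-out. On that reading nobody is lost and the defect is unreconciled wording. This stands as one legitimate reading. It does not remove the point, because sections 5.1, 6.5 and 4.5 say otherwise and the analysis arm is never stated.

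**A large false effect is tempting to infer.** With assumed usual-care screening of 40% under engaged GPs, 20% under others and half of consumers in each group, a reader might compute 40% against 30%, a spurious 10 points. The documents do not support this as an estimate, for two reasons. First, section 4.4 defines the primary endpoints as differences in changes, and Table 9 compares the post-intervention window with two earlier windows. Under those fixed rates both arms show zero change and the false effect is zero. Second, Table 9 lists only GP records for screening. Extraction needs consent and approval (synopsis step 10), and section 5.3 counts the data extract as a paid component of GP participation. A comparison consumer of a declining GP is then probably missing for that outcome, not observed at 20%.

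**A reader might also infer that no analysis could help.** That is too strong: a comparison of changes removes a stable level difference. What remains is a trend that differs by GP engagement, and the wording of section 8.2, which can be read as comparing post-intervention outcomes only. The two filters also still differ, since allowing a data extract is a lower bar than installing software, and the survey outcome needs no GP consent.

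**Conclusion.** The contradiction is established from current text. Followed as written, criterion 4 selects the intervention arm alone on GP engagement, after allocation. That allocation comes first is inferred from the order of the procedure steps and the arm-specific recruitment rules, because no allocation date is given. The study flow chart could not be consulted.

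Bias is possible, but its size and direction cannot be computed: the protocol gives no GP consent rate and no outcome level or trend by GP engagement. It would be small if engaged and other GPs differ only by a stable amount and changes are analysed. It would not be removed if trends differ or if only post-intervention outcomes are compared.

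The point should be settled before the primary analysis because it decides who enters it. The power figures assume equal arms, design effect 2 and no effect where the GP does not consent.

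**What to change.** 1. Remove criterion 4 as an eligibility condition in section 5.1 and the synopsis, so that consumer eligibility is the same in both arms. Treat GP consent and installation as uptake of the intervention.
2. Define the primary intention-to-treat set as all consented consumers, analysed by allocated team whatever the GP decides. Table 2 schedules the end of recruitment for 12/2022, so the change acts mainly through this analysis set, using the consumers whom section 5.3 already follows up.
3. Align synopsis step 5, section 4.5, section 5.3 item 9, and section 8.2, including its receipt-based economic comparator. State in section 8.2 that the primary model estimates the difference in change, as section 4.4 requires.
4. For consumers of declining GPs, use the sources Table 9 already lists: the consumer survey for advice or referral, and HealtheNet for prescriptions. Treat GP-record screening as missing under the same rule in both arms. Table 9 offers no substitute source for screening, and switching source according to GP consent would itself create differential measurement.
5. Restate power for the expected uptake.

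**Cost.** The wording changes are small; the real cost is dilution. On the assumptions above, power falls from 0.83 at full uptake to about 0.75, 0.54 and 0.32 at 90%, 70% and 50%. Screening will also have missing values where GPs refuse data extraction, and these need one stated approach for both arms.

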5.2. EXCLUSION CRITERIA

Consumers:

1. Unable to give informed consent.
2. Unable to speak English or a language supported by the study.

GPs:

1. No EMR

5.3 RECRUITMENT

1. *Who will be recruited?*

Consumers of mental health services in SLHD and their GPs will be recruited to the study. Specifically:

- Adult consumers of the SLHD Adult Community Mental Health 'Core' Teams in Canterbury, Croydon, Camperdown and Marrickville in shared-care arrangements with their GP (or willing to commence shared care arrangements).
- The consumer's general practitioner engaged in shared care with the mental health service.

RECRUITMENT OF CONSUMERS

2. *How will participants be identified and recruited?*

1. SLHD Mental Health Care Coordinators or Shared Care Clinicians ("Clinicians") will introduce the study to the consumer. This could be face-to-face at the clinic (before or during a consultation) or via telephone if the consumer is not visiting the mental health facility during the recruitment period. Interested consumers will be asked whether they agree to see or be contacted by a researcher and, if so, ascertain the appropriate method of contact, e.g. telephone, letter, email or face to face. This verbal approval to be contacted by the researcher and the contact details of the consumer and their GP will be noted by the Clinician in an Excel database in a SLHD MS Teams folder.

The Clinician will provide consumers with a package of information about the study and the researcher's role in the study that contains a short, easy-read information sheet (Appendix 10.5) and a more detailed Information for Participants (Appendix 10.1) that consumers can discuss with significant others (e.g. family, carer, kinship group, support worker).

2. When possible, a researcher will be based at the clinic. If so, interested consumers will be introduced to the researcher. Clinicians will also provide the researcher with the name of the consumer's GP. GP name is necessary at this time so informed consent can be given by the consumer for the researchers to contact that GP.

When a researcher is not at the clinic or is not available, interested consumers will be noted in an Excel Database in a SLHD MS Teams folder and this information will be used by the research team to contact that consumer.

3. *Will the potential participants be screened?*

SLHD Mental Health Care Coordinators will identify if consumers meet eligibility requirements.

The mental illness of consumers will be assessed by the Mental Health Care Coordinators to determine if they have capacity to consent at the time prior to referring to the research team.

Mental Health Care Coordinators will not approach people who are known to have existing guardianship arrangements around medical decision making (for example, people with cognitive impairment or intellectual disability that are sufficient to prevent informed consent).

4. What is the impact of any relationship between researchers and potential participants on recruitment?

Research staff are employed separately to the health services. Research staff will have no prior relationship with consumers. The initial approach about participation will be made by Mental Health staff not directly involved in the research.

5. How will the recruitment strategy facilitate obtaining the consent of participants?

Research staff will be trained to be able to build rapport with mental health service consumers and to be flexible in the recruitment process. It is anticipated that referral to the study by a care co-ordinator will engender trust in the value of the research project. All efforts will be made to minimise participant burden. Consumers will be invited to consult or include carers, support/peer workers or any other trusted person if they would like their assistance with the consent process.

6. How will the recruitment strategy ensure that participants can make an informed decision about participation?

The researcher will verbally explain the information provided on the participant information sheet. A script has been prepared to ensure all key points are addressed and appropriate language is used (Appendix 10.6)

An easy-read information sheet will be available for consumers to read and discuss with significant others (e.g. family, carer, kinship group, support worker) who can assist in deciding whether or not to consent to participating in the study (Appendix 10.5).

7. Are there any risks associated with the recruitment strategy for potential participants or for the viability of the project?

The nature of this study is nonintrusive and there should be no significant risk to participants' physical or mental health. Information about the study will be provided at arms-length from the research by clinical mental health workers who are not involved in the research.

Recruitment and data collection will be via telephone or online meeting (e.g. Zoom) or in community mental health service settings. No recruitment or data collection will involve inpatients in acute hospital settings.

The information and consent process are flexible allowing for verbal consent if the consumer prefers. Consumers can withdraw from the study at any time.

While the interview and focus questions will not be seeking information about the participants' mental illness history or previous traumatic events, there is a risk that any discussion about events and behaviours could trigger past trauma. To minimise risk and ensure support, a protocol will be developed with mental health services. The information sheet includes information about mental health support they can access after the interview if issues arise: their care coordinator and their GP. Participants can choose to take a support person into the interview with them.

Data collection with PWSMI in supported environments decreases risk to the researchers relative to interviewing in participants' homes. Other strategies to mitigate risk to the research officer consistent with the UNSW Fieldwork Guideline (HS406) include: maintaining communication, debriefing, and accessing the Employee Assistance Program if necessary. The research officers engaged to conduct data collection will have experience in data collection with health-service consumers from disadvantaged groups and will receive specific training in data collection with people with mental illness.

Psychological support will be available if consumers become distressed via their mental health team or out of hours services.

Where consumers are admitted to hospital subsequent to approach or recruitment (for physical or mental health issues), we will arrange assessment as soon as possible after discharge, if that is acceptable to the consumer.

8. *Consistency with the requirements outlined in National Statement 4.5.5-11 regarding having respect for participants with a cognitive impairment, an intellectual disability, or a mental illness.*

- Only consumers with the capacity to consent will be invited to participate in the study
- Where the mental illness is temporary or episodic, an attempt will be made to seek consent at a time when the condition does not interfere with the person's capacity to give consent.
- The process of seeking the person's consent will include discussion of any possibility that his or her capacity to consent or to participate in the research may vary or be lost altogether. The participant's wishes about what should happen in that circumstance will be followed.
- The capacity of the consumer to consent to the research will be assessed his/her mental health care coordinator, who is qualified to judge the capacity of their patients. Where there are any concerns, this will be discussed with the consumer's treating psychiatrist.
- Care coordinators will advise the research team of any changes in the participant's capacity to consent and to participate in the research.
- Care has been taken in the design of the interviews and will be taken in the training of interview staff to ensure that the interview does not increase consumer's discomfort or distress and to ensure that, if this were to occur, that the interview would be stopped and the consumer supported and referred appropriately.

RECRUITMENT OF GPs

1. After a consumer has consented to participate in the study (which includes consent to the research team contacting their GP about study participation), the research team will contact the consumer's GP. The name of the GP and their practice will be confirmed with the consumer.
2. If feasible, a letter from the consumer is posted to the GP informing that the consumer has consented to be in the study and inviting the GP to be in the study (Appendix 15.2). The letter states: *"The research team will contact you shortly or you can contact the Research Manager, [name]"*.
3. The GP contact details are recorded by the MH clinician in an Excel database on the SLHD MS Teams folder and shared with the research team.
 - 3.1 Intervention group: Details of GPs who decline will not be retained after data collection has completed. They will be retained during the data collection period because consumers are known to change GPs and this information is likely to be necessary to follow up.
 - 3.2 Comparison group: Details of GPs who decline but whose consumers consent to participate, will be retained. They will be retained because consumers will receive their usual shared care (no need for the GP to install the electronic care plan), and this information is likely to be necessary to follow up.
4. The research team will use a script when they contact the GPs (Appendix 15.4).
5. GPs can consent verbally (Appendix 11.6) or by signing a written consent form (Appendix 11.3). GPs will be offered reimbursement for their participation in the study (\$100 shopping voucher or cash for participating in each component of the study). Recruitment materials include a letter of invitation from the head of the mental health service in the LHD (Appendix 15.1), a letter from the GP's patient informing the GP that s/he has consented to be in the study and inviting the GP to also consent to be in the study (Appendix 15.2), GP participant information abbreviated (Appendix 15.3) and in full (Appendix 10.2).

9. *What happens if a GP does not want to participate?*

If a GP does not want to participate in the trial, neither they nor their patients who are engaged with the mental health service (MHS) will be given access to the online shared-care tool. Consumers of these GPs can still provide baseline data for the study and will be followed up for the study. Communication between the GP and the MHS will continue as usual, which is generally via letters and faxes.

10. How will participants be recruited to the qualitative interview?

Participants from both groups will be invited to participate in semi-structured qualitative interviews. This will include consumers and their carers, and health care providers (including MHS staff and GPs).

Consumers will be invited to express interest in themselves and/or their carers being interviewed for the study via an invitation within the consumer survey. Contact details will be requested so the study team can contact the consumer and/or their carer.

The research team will contact the consumers who expressed interest and any carers who were nominated by consumers to recruit them to the qualitative interviews.

GPs will be invited to express interest in being interviewed for the study via an invitation within the GP survey. A similar process to that for consumers will be used to contact those GPs who expressed interest in being interviewed.

Mental health service care coordinators who have facilitated consumer recruitment to the study will be invited to express interest in being interviewed via a letter of invitation sent to them by the Principal Investigator, [name] (Appendix 13). The letter of information will include a Participant Information sheet (Appendix 10.3) and consent forms for care coordinators (Appendix 11.4). A similar process to that for consumers will be used to ensure that a broader consumer and Provider perspective on shared care is captured.

11. How will participants be reimbursed for their time and expenses for participation in the study?

Consumers will be reimbursed for their time and expenses participating in the baseline survey, follow-up survey and qualitative interview via a \$20 gift voucher per occasion of participation (maximum \$60 per consumer across the course of the study). This amount was deemed reasonable as the survey is designed to be short in duration and additional travel should not be necessary as interviews are expected to be conducted via telephone, zoom, or face-face at the mental health service.

GPs will be reimbursed for their time and expenses participating in the research study via a \$100 shopping voucher (or cash whichever GP prefers) for participating in each of the following components of the study including 1) Baseline survey (15 min), 2) Follow up survey (15 min), 3) Data extract (just access to computer), 4) INCA installation/training (intervention group now and comparison group 3 months after their usual shared care appointments, i.e., 3 months after 30 June 2023) and 5) Qualitative interview (20-30 minutes). Each GP receives total 5, \$100 payment over the study period.

